# **ABBREVIATIONS**

**Table 1** List of Abbreviations

Abbreviation	Definition			
AE	Adverse event			
AESI	Adverse event of special interest			
AIC	Akaike's information criterion			
AKI	Acute kidney injury			
ALP	Alkaline phosphatase			
ALT	Alanine aminotransferase			
ANCOVA	Analysis of Covariance			
AR	First-Order Autoregressive			
AST	Aspartate aminotransferase			
ATC	Anatomical Therapeutic Chemical			
B2M	Beta-2-microglobulin			
BLQ	Below the limit of quantification			
BMI	Body mass index			
CD	Crohn's disease			
CDAI	Crohn's Disease Activity Index			
CDCA	Chenodeoxycholic acid			
CA	Cholic acid			
CLU	Clusterin			
CM	Composite measure			
CMH	Cochran-Mantel-Haenszel			
COVID-19	coronavirus disease 2019			
CRO	Contract Research Organization			
CS	Compound symmetry			
CSR	Clinical Study Report			
CTCAE	Common Terminology Criteria for Adverse Events			
CysC	Cystatin-C			
DCA	Deoxycholic acid			
DILI	Drug-induced liver injury			
D-FIS	Fatigue Impact Scale for Daily Administration			
DMC	Data Monitoring Committee			
DRT	Data Review Team			
ECG	Electrocardiogram			
eCRF	Electronic case report form			
eGFR	Estimated glomerular filtration rate			
EQ-5D-3L	3-Level EuroQol-5D			
FC	Fold change			
GCA	Glycocholic acid			
GDCA	Glycodeoxycholic acid			

Abbreviation	Definition
GCDCA	Glycochenodeoxycholic acid
GLCA	Glycolithocholic acid
GUDCA	Glycoursodeoxycholic acid
HEENT	Head, eyes, ears, nose, throat
IBD	Inflammatory bowel disease
ICF	Informed Consent Form
ICH	International Council for Harmonisation
IL-31	Interleukin-31
IPD	Important Protocol Deviation
IWRS	Interactive Web Response System
KIM-1	Kidney injury molecule-1
LCA	Lithocholic acid
LLOQ	Lower limit of quantification
LS	Least-square
LSMD	Least-square mean difference
MAR	Missing at random
MCMC	Markov Chain Monte Carlo
MedDRA	Medical Dictionary for Regulatory Activities
MI	Multiple imputations
MMRM	Mixed effects model for repeated measures
NAG	N-acetyl-β-D-glucosaminidase
NGAL	Neutrophil gelatinase-associated lipocalin
OCA	Obeticholic acid
OLE	Open-Label Extension
OPN	Osteopontin
PBC	Primary Biliary Cholangitis
PD	Pharmacodynamic
PGI-C	Patient Global Impression of Change
PGI-S	Patient Global Impression of Severity
PK	Pharmacokinetics
PROMIS	Patient-Reported Outcomes Information System
PSC	Primary Sclerosing Cholangitis
Q1	1 st quartile (25 th percentile)
Q3	3 rd quartile (75 th percentile)
SAE	Serious adverse event
SAP	Statistical Analysis Plan
SMQ	Standardized MedDRA Query
TCA	Taurocholic acid
TCDCA	Taurochenodeoxycholic acid
TDCA	Taurodeoxycholic acid
TE	Transient elastography

Abbreviation	Definition
TEAE	Treatment-emergent adverse event
TLCA	Taurolithocholic acid
TTF3	Trefoil Factor 3
TUDCA	Tauroursodeoxycholic acid
UC	Ulcerative colitis
uCR	Urine creatinine
UDCA	Ursodeoxycholic acid
ULN	Upper limit of normal
VAS	Visual analog scale
VEGF	Vascular endothelial growth factor
WHO	World Health Organization
WI-NRS	Worst Itch Numeric Rating Scale

#### 1. INTRODUCTION

The purpose of this Statistical Analysis Plan (SAP) is to provide comprehensive and detailed descriptions of the statistical methods and presentation of data collected for Escient Pharmaceuticals, Inc. Protocol EP-547-201 (Randomized, Double-Blind, Placebo-Controlled Study to Evaluate the Effects of EP547 in Subjects with Cholestatic Pruritus Due to Primary Biliary Cholangitis or Primary Sclerosing Cholangitis). Descriptions of planned analyses are provided in order to avoid post hoc decisions that may affect the interpretation of the statistical analysis. The statistical methods applied in the design and planned analyses of this study are consistent with the International Council for Harmonisation (ICH) guideline Statistical Principles for Clinical Trials (E9) (1998) and Statistical Principles for Clinical Trials: Addendum: Estimands and Sensitivity Analysis in Clinical Trials (E9/R1], Rev 1) (2021).

This SAP will be finalized prior to data analysis and before treatment unblinding and database lock to provide comprehensive details of the tables and listings to be presented in the Clinical Study Report (CSR). Any changes between the statistical methods provided in the clinical study protocol and this SAP will be explained herein; any changes or deviations from this SAP relative to the final analysis will be fully documented in the CSR. Minor changes or deviations from the templates for tables and listings need not be documented in the CSR.

# 2. STUDY OBJECTIVES

# 2.1 Primary Study Objective

The primary objective of this study is to assess the efficacy of EP547 compared to placebo on pruritus as assessed by the Worst Itch Numeric Rating Scale (WI-NRS).

# 2.2 Secondary Study Objectives

The secondary objectives of this study are:

- To assess the efficacy of EP547 compared to placebo on the following:
  - Pruritus-related quality of life using the 5-D Itch Scale
  - Pruritus severity using the Patient Global Impression of Severity (PGI-S)
  - Overall pruritus response to therapy using the Patient Global Impression of Change (PGI-C)
- To assess the safety and tolerability of EP547
- To assess the pharmacokinetics (PK) of EP547

# 2.3 Exploratory Objectives

[figure not shown]
#### 3. INVESTIGATIONAL PLAN

# 3.1 Overall Study Design

EP-547-201 is a randomized, double-blind, placebo-controlled study to evaluate the effects of EP547 on pruritus over 6 weeks in subjects with cholestatic pruritus due to primary biliary cholangitis (PBC) or primary sclerosing cholangitis (PSC). Where allowed per regulatory/local requirements, subjects will be able to attend study visits at a physical study site as well as remotely (hybrid model) or at a virtual site where all visits will be conducted remotely (decentralized model). For both the hybrid and decentralized models, a home health nurse visit at the subject's home or work and a telemedicine visit with the study site staff (e.g., smartphone or computer) will be arranged to conduct procedures for each remote study visit.

The study includes a Screening Period of up to 4 weeks to assess subject eligibility; a 6-week Double-Blind Treatment Period; a 6-week Open-Label Extension (OLE) Period; and a 2-week Safety Follow-Up Period after administration of the last dose of study drug (EP547 or placebo). Approximately 58 subjects with cholestatic pruritus due to PBC or PSC will be randomized to receive either 100 mg doses of EP547 or placebo orally (PO) QD in a 1:1 ratio. In the Open-Label Extension Period, all subjects will receive 100 mg doses of EP547. Details of the study design are presented in Figure 1.

Figure 1 EP-547-201 Study Design

PO = oral, QD = once daily.

<sup>a For the decentralized model, enrollment/randomization and the first dose of study drug may be separated by up to 10 additional calendar days to allow for home delivery of study drug. When enrollment/randomization and first dose of study drug are on separate days, the first dose of study drug is considered Day 1.

<sup>b Any subject who completes the Open-Label Extension Period or discontinues study drug (EP547 or placebo) early will complete a follow-up visit approximately 2 weeks (±3 days) after the last dose of study drug.

The Screening Period will consist of one study visit (Visit 1). During this period, subjects will undergo assessments to determine study eligibility. Visit 1 (Day -28 to Day -1) may be conducted over more than one day but must be completed between Day -28 and Day -1.

The Double-Blind Treatment Period will consist of five study visits (Visits 2, 3, 4, 5, and 6 [Day 1 and Weeks 1, 2, 3, and 6]). During this period, all subjects who meet eligibility requirements will be enrolled into the study and randomized to receive double-blind, PO, QD 100 mg doses of EP547 or placebo for 6 weeks beginning on Visit 2 (Day 1). Visit 2 (Day 1) will not have a visit window; however, for the decentralized model, enrollment/randomization and the first dose of study drug may be separated by up to 10 additional calendar days to allow for home delivery of study drug. When enrollment/randomization and first dose of study drug are on separate days, the first dose of study drug is considered Day 1. All other visits in the Double-Blind Treatment Period will have a visit window of ±3 days.

For the hybrid model, Visits 1, 2, 6, and 8 (Screening, Day 1, Week 6, and Week 12) and early termination (if applicable) must be completed at the study site. All other study visits may be conducted remotely, where allowed per regulatory/local requirements. For the decentralized model, all visits will be conducted remotely.

For remote visits for both the hybrid and decentralized models, the home health nurse visit at the subject's home or work and the telemedicine visit with the study site staff for a given study visit may be conducted on different days but must be within the allowable visit window. The home health nurse will complete the study assessments that the site is physically unable to complete remotely (e.g., blood and lab sample collection, vital signs, electrocardiograms [ECGs]); the site will complete all other study assessments remotely during the telemedicine visit.

The Open-Label Extension Period will consist of two study visits (Visit 7 [Week 9] and Visit 8 [Week 12]). During this period, all subjects who complete the Double-Blind Treatment Period and are still receiving study drug will receive open-label 100 mg doses of EP547. Visit 7 and Visit 8 will have a visit window of ±3 days.

Any subject who completes the Open-Label Extension Period or discontinues study drug (EP547 or placebo) early will complete a Follow-Up Visit (Visit 9) approximately 2 weeks (±3 days) after the last dose of study drug.

#### 3.2 Schedule of Assessments

For the complete schedule of assessments, refer to Appendix A of the clinical study protocol.

#### 3.3 Treatments

#### 3.3.1 Treatments Administered

Tablets containing 25 mg or 75 mg of EP547 or placebo will be supplied in a way to ensure the study blind. For the Open-Label Extension Period, tablets containing 25 mg and 75 mg of EP547 will be supplied. Subjects receiving EP547 will take one 25 mg

and one 75 mg EP547 tablet per dose (for a total dose of 100 mg) and subjects receiving placebo will take two placebo tablets per dose.

Each study drug dose, containing two tablets, is to be administered orally as intact tablets (swallowed whole, not chewed or crushed), and taken with water. Doses are to be administered daily at approximately the same time of day after a fast of at least eight hours.

EP-547-201 treatment assignments by study period are presented in Table 2.

**Table 2 EP-547-201 Treatment Assignments** 

Study Period	Study Days	Approx. No. of Subjects	Treatment Designation	Study Drug Dose Regimen
Screening	Day -28 to Day -1	58	Not applicable	None
6-Week, Double-	Day 1 to Day 42	29	100 mg EP547	One 25 mg EP547
Blind Treatment				tablet and One 75 mg
				EP547 tablet PO QD
		29	Placebo	Two placebo tablets
				PO QD
6-Week, Open-	Day 43 to Day 85	58	100 mg EP547	One 25 mg EP547
Label Extension				tablet and One 75 mg
				EP547 tablet PO QD
2-Week Safety	2 weeks after last	58	Not applicable	None
Follow-Up	study drug dose			

 $\overline{PO} = \text{oral}; QD = \text{once daily}.$ 

#### 3.3.2 Prohibited Concomitant Medications

Subjects taking immunosuppressant/immunomodulating agents may not receive live, attenuated vaccines during participation in this study. Medications with known nephrotoxic potential (e.g., aminoglycosides, contrast dye, bisphosphonates, and nonsteroidal anti-inflammatory drugs) are prohibited from use during the study as are some medications that are substrates for BCRP, OAT1, CYP2B6, or CYP2C8, or inhibitors of OAT3. Table 3 of the clinical study protocol lists examples of excluded medications that are substrates for BCRP, OAT1, CYP2B6 or CYP2C8, or inhibitors of OAT3. If a subject receives a prohibited concomitant medication during the study, the Investigator, in consultation with the Medical Monitor, may interrupt or discontinue study drug as warranted for reasons of protecting subject safety.

#### 3.3.3 Method of Assigning Subjects to Treatment Groups

All subjects who meet eligibility requirements will be enrolled into the study and randomized to receive double-blind, PO, QD doses of EP547 or placebo for 6 weeks beginning at Visit 2 (Day 1). Subjects will be randomized to receive either 100 mg doses of EP547 or placebo in a 1:1 ratio. Randomization will be conducted centrally via an Interactive Web Response System (IWRS) and stratified based on type of cholestatic disease (PBC or PSC).

All subjects who complete the Double-Blind Treatment Period and are still receiving study drug will receive open-label 100 mg doses of EP547 during the Open-Label Extension Period.

# 3.3.4 Blinding Procedures

The Sponsor, Medical Monitor, Contract Research Organization (CRO) staff, Investigators, site staff, and subjects will be blinded to subject's assigned treatment during the Double-Blind Treatment Period of the study until the database is locked except for CRO or vendor staff involved in the analysis of PK samples or safety reporting to regulatory agencies.

To address business needs, a limited number of study team members and senior stakeholders comprising the internal Data Review Team (DRT) may conduct and review an interim analysis of all accumulated data including unblinded data from the Double-Blind Treatment Period (see Section 4.4.7.3). The rest of the central study and project team members will remain blinded.

Treatment with 100 mg doses of EP547 during the Open-Label Extension Period will be conducted in an unblinded manner.

If an emergency unblinding during the Double-Blind Treatment Period is required, the subject's treatment assignment may be unblinded through IWRS by the Investigator. If a treatment assignment is unblinded, the subject will be discontinued from randomized treatment. Blinding codes should only be broken in emergency situations for reasons of subject safety and when knowledge of the treatment assignment will impact the clinical management of the subject. Every reasonable attempt should be made to complete the post-treatment evaluation procedures prior to unblinding as knowledge of the treatment arm could influence subject assessment.

In all emergency cases, the reasons and rationale for unblinding will be documented in writing and maintained in the study file.

Access to randomization codes and corresponding treatment assignment will also be made available through the IWRS system to the appropriate individual(s) responsible for unblinding suspected unexpected serious adverse reactions for reporting to the Regulatory Authorities.

# 3.4 Efficacy and Safety Variables

# 3.4.1 Efficacy Variables

#### 3.4.1.1 Primary Efficacy Variable

The primary efficacy endpoint is the change from baseline in WI-NRS at Week 6.

Subjects will be asked to rate the severity of their worst level of itching in the past 24 hours in the morning, and at the same time of day, using the WI-NRS. The WI-NRS is an 11-point scale ranging from 0 (No Itching) to 10 (Worst Itching Imaginable) (Phan 2012) and requires approximately 1 minute to complete. Higher scores indicate greater itch severity. Itching severity scores collected via the WI-NRS have been categorized in the literature as mild (<4), moderate (≥4 to <7), or severe (≥7) (Fishbane 2020, Hirschfield 2020, Levy 2020, Stander 2020).

Subjects will be instructed to complete the WI-NRS daily, in the morning, and at the same time of day, beginning at Day -14 to the Follow-Up Visit. For days that coincide with a study visit (for Visit 2 and beyond), the WI-NRS is to be completed before the visit.

For WI-NRS, a weekly score will be determined based on the average of all available daily scores of the week. Weekly scores will be calculated for Week 1 through Week 6 of the Double-Blind Treatment Period and Week 7 through Week 12 of the Open-Label Extension Period. During the Safety Follow-up Period, weekly scores for Week 13 and Week 14 will be derived, when available.

The average WI-NRS score using the daily values from the week before the first dose of study drug (including the WI-NRS score captured on study day 1 of dosing) will serve as the baseline score.

For subjects who complete the nominal Week 6 visit, the weekly WI-NRS scores for both the Double-Blind Treatment Period and Open-Label Extension Period will be anchored to the nominal Week 6 visit date with the following considerations applied:

- Within the Double-Blind Treatment Period, analysis of Week 6 will be the 7 days leading up to the nominal Week 6 date (including the nominal Week 6 visit date WI-NRS score). Each preceding analysis visit will be the 7 prior days.
- Within the Open-Label Extension Period, analysis of Week 7 will be the first 7 days after the nominal Week 6 visit date or start date of open-label dosing, whichever is later; for subjects who participate in the decentralized model, there may be a gap between the nominal Week 6 visit and open-label dosing due to drug shipment considerations. Subsequent analysis visits will be counted using the next 7 days. The Week 6 WI-NRS score will be used as the Initiation of OLE score.

The Safety Follow-up Period will be anchored to the nominal Week 12 visit date. Week 13 will be the first 7 days after the nominal Week 12 visit date and Week 14 will be derived using the next 7 days.

For subjects who early terminate during the Double-Blind Treatment Period, the subject's first day of dosing (i.e., study day 1) will be the anchor date for weekly analysis visit derivations. Week 1 will be study days 2 through 8 and subsequent weekly analysis visits will be the next 7 days, deriving all applicable analysis visits until early termination.

The following additional general considerations will be applied in deriving the weekly WI-NRS scores:

- No WI-NRS daily score is to be utilized in more than one analysis visit derivation.
- For weeks where 7 calendar days are available for a given week, there must be 4 non-missing daily scores to compute the weekly score; if more than 3 daily scores are missing, the weekly score is considered missing.

• For weeks where less than 7 calendar days are available for a given week due to visit anchoring rules, at least 57% of the daily scores for the available calendar days must be reported, maintaining the same rate of reported scores as seen for a full week (i.e., 4 out of 7 days). If 6 calendar days are available for a given week, 4 non-missing daily scores are required. If 4 or 5 calendar days are available for a given week, 3 non-missing daily scores are required. If less than 4 calendar days are available for a given week, the weekly score will be considered missing.

A bi-weekly WI-NRS score will be calculated for exploratory analysis. The average WI-NRS score using the daily values from the 14 days before the first dose of study drug (including the WI-NRS score captured on the study day 1 of dosing) will serve as the baseline bi-weekly score.

Bi-weekly WI-NRS scores for Week 2, Week 4, and Week 6 in the Double-Blind Treatment Period and Week 8, Week 10, Week 12 in the Open-Label Extension Period and Week 14 in the Safety Follow-up Period will be calculated following the same general guidelines as the weekly WI-NRS scores, applied to a bi-weekly derivation (e.g., requiring 8 non-missing daily scores in 14 calendar days). For intervals shorter than 14 calendar days due to visit anchoring rules, at least 57% of the daily scores for the available calendar days must be reported for a bi-weekly score to be computed. The Change from OLE summary will be relative to the bi-weekly score prior to the Initiation of OLE (e.g., Week 6).

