**APPENDIX A. SCHEDULE OF ASSESSMENTS**

Assessment	Screening	Double-Blind Treatment					Open-Label Extension		Follow-Up	Early Study Term	Notes
		Visit 2 Day 1	Visit 3 Week 1	Visit 4 Week 2	Visit 5 Week 3	Visit 6 Week 6	Visit 7 Week 9	Visit 8 Week 12			
Study Day	Days -28 to -1	Day 1	Day 8	Day 15	Day 22	Day 43	Day 64	Day 85	2 weeks (±3 days) after last dose	≤2 days after last dose	
Visit Window	None	None b	±3 days	±3 days							
Visit Type for Hybrid Model c	Site only	Site only	Site or Remote	Site or Remote	Site or Remote	Site only	Site or Remote	Site only	Site or Remote	Site only	
General Assessments											
Informed consent	X										
Medical history	X										
Height	X										Measured with no shoes.
HIV, HAV, HBV, HCV, HEV serology	X										
IgG4	X										
Eligibility check	X	X									
Randomization via IWRS		X									Subjects will be randomized in a 1:1 ratio to 100 mg EP457 or placebo.
Dispense study drug / administer dose		X			X	X	X				Administer study drug QD as intact tablets with water. For remote visits, study drug dispensing will be conducted by a direct-to-patient courier service.
Collect study drug / assess study drug accountability and compliance					X	X	X	X		X	For remote visits, study drug collection will be conducted by a direct-to-patient courier service.
Provide questionnaire training	X										To be conducted before completing the daily WI-NRS for Day -14.

Assessment	Screening	Double-Blind Treatment					Open-Label Extension		Follow-Up	Early Study Term	Notes
Visit	Visit 1 a	Visit 2 Day 1	Visit 3 Week 1	Visit 4 Week 2	Visit 5 Week 3	Visit 6 Week 6	Visit 7 Week 9	Visit 8 Week 12	Visit 9		
Study Day	Days -28 to -1	Day 1	Day 8	Day 15	Day 22	Day 43	Day 64	Day 85	2 weeks (±3 days) after last dose	≤2 days after last dose	
Visit Window	None	None b	±3 days	±3 days							
Visit Type for Hybrid Model c	Site only	Site only	Site or Remote	Site or Remote	Site or Remote	Site only	Site or Remote	Site only	Site or Remote	Site only	
Efficacy Assessments											
WI-NRS	X	X	X	X	X	X	X	X	X	X	To be completed daily, in the morning, and at the same time of day, from Day -14 to the Safety Follow-Up Visit. For days that coincide with a study visit (for Visit 2 and beyond), it is to be completed before the visit.
5-D Itch Scale		X				X		X	X	X	
PGL-C						X		X		X	
PGL-S		X				X		X		X	
Pharmacodynamic Assessments											
Bile acids and heme metabolites		X				X					

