# 4.1.3 Summarization by Visit

Assessments that are collected only at study visits (i.e., all study assessments except WI-NRS) are to be summarized by study visit and will be based on the nominal, scheduled visit label as reported on the eCRF.

Subjects who discontinue from the study early will have their assessments conducted at the early termination visit mapped and summarized with the next scheduled nominal visit, according to the schedule of events, based on the last visit completed per protocol.

Any subject who completes the Open-Label Extension Period or discontinues study drug (EP547 or placebo) early will complete a Follow-Up Visit (Visit 9) approximately 2 weeks (±3 days) after the last dose of study drug. The Follow-Up Visit may be summarized in both the Double-Blind Treatment Period and Open-Label Extension Period summaries, based on the treatment period of participation at the time of study termination or completion and as warranted by available data.

Data collected at unscheduled visits will not be included in by-visit summaries, but will be considered when endpoint derivations potentially include multiple visits (e.g., determination of baseline value, determination of worst post-baseline value, etc.). All data will be included in subject listings.

For details on WI-NRS analysis visits, see Section 3.4.1.1.

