# 4.4.7.2 Handling of Dropouts or Missing Data

Treatment groups will be compared for observed and change from baseline in weekly WI-NRS score during the Double-blind Treatment Period using a MMRM to include fixed effects for treatment, type of cholestatic disease (PBC, PSC), week, and treatment by week interaction, with the relevant baseline value included as a covariate. A similar model will be used for the exploratory analysis of bi-weekly WI-NRS scores, replacing the week score with a bi-weekly score in the model.

As a sensitivity analysis of the primary endpoint, subjects missing data will be imputed using MI methodology using the subjects in the Full Analysis Set. The MI will be performed under the assumption data is missing at random (MAR) using the model defined in the primary analysis. Using the general methodology described in Ouyang (2017), the following imputations will be applied:

- Intermittent missing value(s) arising prior to a discontinuation event (i.e., discontinuation of randomized treatment or early permanent dropout) are imputed using the Markov Chain Monte Carlo (MCMC) option in SAS PROC MI by treatment group assuming nonmonotone missing, a seed of 671982, 500 burn-in iterations, 100 iterations between imputations, and a non-informative prior. The MAR assumption is reasonable for intermittent missing values as the values of the endpoint before and after the intermittent missing value are known. The imputation of the intermittent missing data will be accomplished using the MCMC option in SAS PROC MI to impute intermittent missing data without a monotone missing pattern, prior to performing imputations of values following the discontinuation event.
- Missing data following a discontinuation event will then be imputed by treatment group under the assumption of MAR using the regression option from the monotone statement of SAS PROC MI. The baseline and post-baseline derived weekly visits during the Double-Blind Treatment Period will be used in the regression option to impute the missing values.
- The MI methods described above will be used to generate 30 imputed datasets. Data will be analyzed using the primary MMRM model for the observed and imputed data; observed and change from baseline values to each post-baseline week visit will be calculated based on observed and imputed data.

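### Does the undefined cut-off for weekly WI-NRS scores in early terminators discard diary data that the treatment-policy estimand needs?

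*SAP*

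**What the plan says.** SAP section 3.4.1.1 gives two anchors for the weekly scores of the double-blind period. One begins "For subjects who complete the nominal Week 6 visit, the weekly WI-NRS scores" and counts back from that visit. The other begins "For subjects who early terminate during the Double-Blind Treatment Period" and counts forward from study day 1, with Week 1 as days 2 to 8, after which "subsequent weekly analysis visits will be the next 7 days, deriving all applicable analysis visits until early termination". No later window can hold an early terminator's scores. Weeks 7 to 12 start from the Week 6 visit or open-label dosing, and for Weeks 13 and 14 "The Safety Follow-up Period will be anchored to the nominal Week 12 visit date".

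SAP section 4.1.3 assigns early termination visit data to the next scheduled visit, but only for "all study assessments except WI-NRS", and refers WI-NRS back to 3.4.1.1.

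The protocol schedule (Appendix A) times the early termination visit at "≤2 days after last dose". The Follow-Up Visit is a separate column, about 2 weeks (±3 days) after last dose. Protocol sections 9.4.4.1 and 11.1.1 continue the daily WI-NRS to the Follow-Up Visit. Protocol section 14.2 and SAP section 4.4.3 adopt a treatment-policy strategy, so scores after drug discontinuation count.

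**The concern.** Early termination is not defined, and two readings are possible.

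- **Visit reading.** The cut-off is the early termination visit. Protocol section 8.5.1 asks for those evaluations from anyone who stops drug, and section 9.4.5 times the visit just after the last dose.
- **Exit reading.** The cut-off is the end of participation, so the diary counts as far as it goes, up to study day 43.

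Under the visit reading, up to about two weeks of off-drug scores are collected but used in no week. The MMRM and the multiple-imputation analysis would then fill the later weeks under missing at random, mainly from on-drug scores. If benefit fades after stopping, the Week 6 difference would be overstated. Two programmers could also derive different primary data for the same subject.

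There is a second gap. A subject who misses the Week 6 visit but stays in the study fits neither anchor as worded.

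**Working it through.** **1. Subjects concerned.** SAP section 4.6 plans 26 completers per arm with 10% early withdrawal: 26 / (1 − 0.10) = 28.9, rounded up to 29, which reproduces the plan. Expected withdrawals are 0.10 × 29 = 2.9 per arm. Subjects who stop drug but complete the Week 6 visit use the Week 6 anchor and are unaffected. After consent withdrawal no further data are collected (protocol section 8.5.2).

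**2. Derivable weeks.** Week k covers study days 7k − 5 to 7k + 1. With a complete diary, four days are needed, so the diary must reach day 7k − 2. Assumptions: last dose uniform over Days 1 to 42; diary to last dose + 2 under the visit reading and to last dose + 14 under the exit reading. The table counts last-dose days, out of 42, for which each week can be derived.

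| Week | Diary must reach day | Visit reading | Exit reading |
|---|---|---|---|
| 1 | 5 | 40 | 42 |
| 2 | 12 | 33 | 42 |
| 3 | 19 | 26 | 38 |
| 4 | 26 | 19 | 31 |
| 5 | 33 | 12 | 24 |
| 6 | 40 | 5 | 17 |
| Sum | | 135 | 194 |

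Mean weeks per subject: 135/42 = 3.2 against 194/42 = 4.6. For Week 6 under the exit reading, the ±3-day follow-up window gives 14 to 20 in place of 17. Example: a last dose on Day 28 gives Weeks 1 to 4 under the visit reading and Weeks 1 to 6 under the exit reading.

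**3. Week 6 scores that depend on the reading.** (17 − 5)/42 × 2.9 = 0.83 per arm. The window gives (14 − 5)/42 × 2.9 = 0.62 to (20 − 5)/42 × 2.9 = 1.04. If half the stoppers stay to Week 6, 0.83 falls to 0.41. If in addition only half of the leavers keep the diary, it falls to 0.21.

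**4. Effect on the Week 6 difference.** This comes from a large-sample simulation of the MMRM (100,000 per arm, 6 replicates, disease stratum omitted). The SD of 2.5 and the 10% are the plan's. Assumed: on-drug effect 2.0, AR(1) correlation 0.85 between weeks, baseline SD 1.5 with slope −0.4, benefit lost from the day after last dose.

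| Scenario | Full Week 6 data | Visit reading | Exit reading | Visit minus exit |
|---|---|---|---|---|
| Moderate: half stay, half the benefit lost, half keep diaries | 1.909 | 1.944 | 1.930 | 0.014 |
| Extreme: nobody stays, all benefit lost, full diaries | 1.82 | 1.96 | 1.85 | 0.11 |

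The last column is the relevant one. The remaining distance to full data (0.021 and 0.03) comes from scores after the Follow-Up Visit, which are never collected from people who leave. If benefit persists, the bias is about 0.

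**5. Scale.** SE = 2.5 × √(2/29) = 0.66. So 0.014/0.66 = 0.02 SE and 0.11/0.66 = 0.17 SE.

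**6. Range.** For effects of 1 to 3 and 5% to 15% stopping, total bias under the visit reading is 0.01 to 0.07 (moderate) and 0.04 to 0.32 (extreme). That is close to proportional to effect times stopping rate. Scaling the part that depends on the reading in the same way gives 0.014 × 0.25 = 0.004 to 0.014 × 2.25 = 0.03 (moderate), and 0.11 × 0.25 = 0.03 to 0.11 × 2.25 = 0.25 (extreme). With correlation 0.60 or 0.95, total bias is 0.039 or 0.032 (moderate) and 0.16 or 0.13 (extreme).

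**7. Which reading the documents support.**
- SAP section 4.4.3 includes data from subjects who stop drug early. The visit reading contradicts this; the exit reading does not.
- SAP section 4.1.3 ties the early termination visit to leaving the study: "Subjects who discontinue from the study early will have their assessments conducted at the early termination visit". It also speaks of study termination when assigning the Follow-Up Visit to a period.
- SAP section 4.5, on safety, uses termination for the point at which a non-completer's data end.
- Where the SAP means stopping drug it says so, as in section 4.4.7.2: "discontinuation of randomized treatment or early permanent dropout".
- Protocol section 7.2 makes the Follow-Up Visit the last study visit.

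**The case for a change.** The strongest argument for acting is that this rule builds the primary endpoint, and SAP section 1 says the plan exists to prevent post hoc decisions. Protocol sections 8.5.1 and 9.4.5 and the separate schedule column keep the visit reading possible. The SAP usage cited for the exit reading comes from safety text and from a section that excludes WI-NRS, so it shows how the word is used and sets no rule. The imputation analysis could not reveal a loss, because it works on the same derived weeks. Responder analyses use observed values only (SAP sections 4.4.4.2 and 4.4.7.2), so a subject without a Week 6 score drops out of the denominator. The missed-visit gap exists under either reading.

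Part of this stands: the term is undefined and the missed-visit case is not addressed. The visit reading, however, requires the analyst to set aside the stated estimand. The responder denominators change by the same one score or fewer per arm. For a subject who misses the Week 6 visit, study day 1 is the only other anchor offered. Open-label drug is dispensed at that visit, so the case mainly concerns people already off drug.

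A further wrinkle is that the short-week rule in SAP section 3.4.1.1 names only weeks shortened by visit anchoring. It is therefore unclear whether three scores suffice in a week of four or five days cut short by the last diary entry. With four scores present, both rules agree, so the counts above do not depend on it.

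**Conclusion.** No change to the plan is needed. This is missing detail that an analyst working from the estimand would fill sensibly: weeks counted from study day 1 for as long as the diary runs, on or off drug, up to Day 43. The harm arises only under a reading that conflicts with the SAP's own primary analysis.

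Even then the stake is about 0.8 Week 6 scores per arm at most at the nominal follow-up date, and 0.014 to 0.11 points on the Week 6 difference (0.02 to 0.17 SE). The upper figure needs every stopper to leave, all benefit to vanish the next day and every leaver to keep a complete diary. Stretching the assumed effect to 3 and stopping to 15% takes that extreme to about 0.25 points, or 0.25/0.66 = 0.38 SE.

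The counts assume complete diaries and uniformly distributed last-dose days. The shifts also rest on the assumed effect, correlation and baseline values, since only the SD of 2.5 and the 10% withdrawal rate stand in the plan.
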